4.1 If you indicated other, describe.

5.0 *Attach copies of the informed consent documents, information sheets, consent scripts as applicable to this study. Include copies of translated forms, if applicable.

Document Name	Document Version #
Namenda Consent 11-21-2014 marked.docx	0.01
Namenda Consent 11-21-2014.docx	0.01

Warning: Save your work at least every 15 minutes by clicking "Save" or "Continue."

Cultural Considerations

The following items are designed to acquaint the IRB with cultural features of the population that you are studying that may require procedures to ensure truly informed consent.

1.0 *Check all that apply to the population(s) with which this study will be conducted.

- Participants may be illiterate or insufficiently literate to be able to comprehend a conventional written informed consent form.

- The participants may be reluctant or unwilling to sign a written informed consent form.
- The husbands make decisions for their wives.
- Elders make decisions for younger adult family members.
- Elders make decisions for their community.
- It is considered impolite to refuse a request.
- People are fearful of refusing requests that they regard as coming from authorities.
- None of the above are applicable to this study.**

1.1 If any of the above items are applicable to this study, indicate the steps that you will take to ensure voluntary participation after providing the study information, and if applicable, any planned involvement with the community regarding the consent process.

ID: IRB#12-001714

View: NEW 24.0 - Additional Information and/or Attachments

Warning: Save your work at least every 15 minutes by clicking "Save" or "Continue."

Additional Information and/or Attachments

1.0 Attach any other documents that have not been specifically requested in previous items, but are needed for IRB Review.

Document Name	Document Version #
Risk chart for Memantine or Escitalopram.docx	0.01

2.0 If there is any additional information that you want to communicate about this study, include it in the area provided. Note: this section should not be used instead of the standard application items.

ID: IRB#12-001714

View: NEW 100.0 - Instructions for Study Submission

Instructions for Study Submission

You have completed your application, **but it has *not yet been submitted***.

FOLLOW THESE STEPS TO SUBMIT THE APPLICATION TO THE IRB FOR REVIEW:

1. Click the **Finish** button to return to exit the SmartForm and return to the study workspace.
2. Use the **View SmartForm Progress** function to make sure that the application is complete.
3. If you are the **PI** or **PI Proxy**, click **Submit Study** under **My Activities**. If you are a member of the study team, you can let the PI know that the study is ready to submit by clicking **Send Ready Notification**.
4. Once the study is submitted, the state indicator at the top of the page will no longer display **Pre-Submission**.
5. After submission of the study, the **PI Assurances** activity will immediately become available under **My Activities**. The PI should provide his/her assurances at that time. If the PI is not available, the study can be submitted by a PI Proxy and the assurances provided at a later time. The study will be reviewed by the IRB while the **PI Assurances** are pending; however, it will not be approved until the **PI assurances** are completed.
6. **If there is a Faculty Sponsor for the study:** The study can not be submitted to the IRB until the Faculty Sponsor provides his/her assurances through **FS Assurances** activity.

ID: IRB#12-001714

View: Display - Method Description

Audio, Visual or Digital Recordings

Click "OK" below to return to the SmartForm page where you can select the appropriate response.

ID: IRB#12-001714

View: Display - Method Description

Certificate of Confidentiality for research not supported by NIH

The Certificate of Confidentiality button in this section is only if your study is NOT supported or conducted by NIH but you will obtain a Certificate of Confidentiality (for example, for studies collecting information about illegal drug use).

If you previously checked this box for an NIH-supported study before the policy change, you do not need to change your response here.

Certificates of Confidentiality are issued by the National Institutes of Health (NIH) to protect the privacy of research subjects by protecting investigators and institutions from being compelled to release information that could be used to identify subjects with a research project. Certificates of Confidentiality are issued to institutions or universities where the research is conducted. They allow the investigator and others who have access to research records to refuse to disclose identifying information in any civil, criminal, administrative, legislative, or other proceeding, whether at the federal, state, or local level.

Effective October 1, 2017, NIH has updated its policy for issuing Certificates of Confidentiality for NIH-funded and conducted research. For information about the policy change or about obtaining Certificates for research supported by other agencies, please see <https://humansubjects.nih.gov/coc/index>.

Click "OK" below to return to the SmartForm page where you can select the appropriate response.

ID: IRB#12-001714

View: Display - Method Description

Clinical Trial of a Drug, Biologic, Device or a Behavioral Intervention

A clinical trial is a research study designed to answer specific questions about medical or behavioral treatments. The trial may be interventional or observational. Interventional studies are those in which the research participants are assigned by the investigator to a treatment or other intervention, and the outcomes measured. Observational studies are those in which individuals are observed and the outcomes are measured by the investigators.

Click "OK" below to return to the SmartForm page where you can select the appropriate response.

ID: IRB#12-001714

View: Display - Method Description

Community Based Research

Click "OK" below to return to the SmartForm page where you can select the appropriate response.

ID: IRB#12-001714

View: Display - Method Description

Controlled Substances (Schedule I or II)

Check here only if you are using a Schedule I or II Controlled substance in this study. Research using Schedule I or Schedule II controlled Substances must be submitted to the Research Advisory Panel of California for review and approval prior to initiation. Research using Schedule III, IV, or V Controlled Substances as a study drug do not require review by the Research Advisory Panel. For further information see: <http://ag.ca.gov/research/guide.php> o Schedule I Controlled Substances are drugs or substances with a high potential for abuse, that have no currently accepted medical use in treatment in the United States. Examples of Schedule I Controlled Substances are: heroin, lysergic acid diethylamide (LSD), methylenedioxy-methamphetamine (MDMA), marijuana, and psilocybin. o Schedule II Controlled Substances are drugs or substances with a high potential for abuse, that have a currently accepted medical use in treatment in the United States, or a currently accepted medical use with severe restrictions. Examples of Schedule II

Controlled Substances are: fentanyl, methadone, methylphenidate, morphine, and oxycodone. For further information see: <http://www.deadiversion.usdoj.gov/schedules/index.html>

Click "OK" below to return to the SmartForm page where you can select the appropriate response.

ID: IRB#12-001714

[View: Display - Method Description](#)

Deception or Partial Disclosure

Deception includes withholding information about the real purpose of the study or purposely giving subjects false information about some aspect of the research to prevent bias. Some professions, such as the American Psychological Association (APA) have ethical codes regarding the use of deception in research. (See sections 8.07 and 8.08 at <http://www.apa.org/ethics/code/index.aspx#807>) If deception is included in the study, you must also apply for approval of a waiver of the informed consent process (Section 20.1) in addition to selecting the other consent procedures planned for the study (e.g., written or oral consent).

Click "OK" below to return to the SmartForm page where you can select the appropriate response.

ID: IRB#12-001714

[View: Display - Method Description](#)

Devices/Diagnostics (including Humanitarian Devices - HUD)

A medical device is defined, in part, as any health care product that does not achieve its primary intended purposes by chemical action or by being metabolized. Medical devices include, among other things, surgical lasers, wheelchairs, sutures, pacemakers, vascular grafts, intraocular lenses, and orthopedic pins. Medical devices also include diagnostic aids such as reagents and test kits for in vitro diagnosis (IVD) of disease and other medical conditions such as pregnancy. For further information see: <http://www.fda.gov/oc/ohrt/irbs/irbreview.pdf>

Click "OK" below to return to the SmartForm page where you can select the appropriate response.

ID: IRB#12-001714

[View: Display - Method Description](#)

Drugs/Biologics/Dietary Supplements

- Drug: The term "drug" means: articles recognized in the official United States Pharmacopoeia, official Homoeopathic Pharmacopoeia of the United States, or official National Formulary, or any supplement to any of them; and articles intended for use in the diagnosis, cure, mitigation, treatment, or prevention of disease in man or other animals; and articles (other than food) intended to affect the structure or any function of the body of man or other animals.
- Biologics vs. Drugs: Most drugs consist of pure chemical substances and their structures are known. Most biologics, however, are complex mixtures that are not easily identified or characterized. Biological products differ from conventional drugs in that they tend to be heat-sensitive and susceptible to microbial contamination. This requires sterile processes to be applied from initial manufacturing steps. For more information see: <http://www.fda.gov/consumer/updates/biologics062608.html#drugs>
- Dietary Supplements are products that are intended to supplement the diet and have one of the following ingredients:
 - A vitamin
 - A mineral
 - An herb or other botanical
 - An amino acid
 - A dietary substance for use by man to supplement the diet by increasing the total daily intake
 - A concentrate, metabolite, constituents, or an extract of combinations of these ingredients.

For additional information see: <http://www.foodsafety.gov/~dms/supplmnt.html>

Click "OK" below to return to the SmartForm page where you can select the appropriate response.

ID: IRB#12-001714

[View: Display - Method Description](#)

Expanded Access to Drug, Device or Biologic for Treatment Purposes (aka Compassionate Use, Treatment Use)

Click "OK" below to return to the SmartForm page where you can select the appropriate response.

ID: IRB#12-001714

View: Display - Method Description

Genetic Analyses/Genotyping

Genetic analyses/genotyping include, but are not limited to, studies of inheritable conditions or traits, gene markers or mutations, and pedigrees.

Click "OK" below to return to the SmartForm page where you can select the appropriate response.

ID: IRB#12-001714

View: Display - Method Description

Human Embryonic Stem Cells and/or Induced Pluripotent Stem Cells

Research with human embryonic stem cells (hESC) and related lines requires IRB review under the following conditions:

- o Clinical research in which human subjects are given hESCs or related products.
- o When the UCLA research team will have a research related direct interaction or intervention with the cell donors, including donation of blastocysts or gametes for the purpose of creating hESCs,.
- o Cells provided to the UCLA research team that have identifiers or codes that can be linked back to the donor. Research involving hESC requires review and approval by the ESCRO Committee. For further information see: <http://www.stemcell.ucla.edu/research>

Click "OK" below to return to the SmartForm page where you can select the appropriate response.

ID: IRB#12-001714

View: Display - Method Description

Human Gene Transfer/ Recombinant DNA

Studies involving gene transfer and/or recombinant DNA require approval of the UCLA Institutional Biosafety Committee (IBC) and the NIH Recombinant DNA Advisory Committee (RAC) . Human gene transfer is an investigational method for correcting defective genes responsible for disease development through one of the following techniques:

- o A normal gene may be inserted into a nonspecific location within the genome to replace a nonfunctional gene.
- o An abnormal gene could be swapped for a normal gene.
- o The abnormal gene could be repaired through selective reverse mutation, which returns the gene to its normal function.
- o The regulation of a particular gene could be altered. Recombinant DNA molecules, according to the NIH Guidelines, are defined as either: (i) molecules that are constructed outside living cells by joining natural or synthetic DNA segments to DNA molecules that can replicate in a living cell, or (ii) molecules that result from the replication of those described in (i) above.

Click "OK" below to return to the SmartForm page where you can select the appropriate response.

ID: IRB#12-001714

View: Display - Method Description

Infectious Agents

Studies involving the use of Risk Group 2 or 3 infectious agents (such as bacteria, fungi, parasites, prions, rickettsia, viruses, etc.) require approval of the UCLA Institutional Biosafety Committee (IBC).

Click "OK" below to return to the SmartForm page where you can select the appropriate response.

ID: IRB#12-001714

View: Display - Method Description

Non-FDA approved medical equipment used with UCLA hospital patients or research participants that operate under the UCLA Hospital License.

Clinical Engineering is responsible for completing incoming inspections on investigational devices that are used to diagnose, treat or monitor a patient and that are used in the patient care area on site at UCLA, but *not* in other hospitals such as Cedars Sinai, CHLA, or Drew. If a device is FDA and/or testing - laboratory approved for the purpose it was designed, then evaluation is not required of the device. If you have a copy of an inspection report from Clinical Engineering, please attach here. As appropriate, please contact Clinical Engineering at [contact] to arrange an inspection.

Click "OK" below to return to the SmartForm page where you can select the appropriate response.

ID: IRB#12-001714

View: Display - Method Description

Radiation (Standard of Care or Investigational Use of radioactive materials, radiation producing machines or ionizing radiation)

Note: This includes CT-guided biopsy, fluoroscopy use, etc.; MRI is not included. The radiological procedures included in this study must be described in the SafetyNet system. Please create a new SafetyNet application after submitting this webIRB application to the IRB for review.

Click "OK" below to return to the SmartForm page where you can select the appropriate response.

ID: IRB#12-001714

View: Display - Method Description

Substance Abuse Research (with Medication)

Research for the treatment of controlled substance addiction or abuse that uses any drug (scheduled or not) as treatment, requires the review and approval of the Research Advisory Panel of California prior to initiation. For further information see: For further information see: <http://ag.ca.gov/research/guide.php>

Click "OK" below to return to the SmartForm page where you can select the appropriate response.

ID: IRB#12-001714

View: Display - Method Description

Treatment in an Emergency Setting (with request to waive consent)

Federal regulations allow certain research activities to be conducted in emergency settings with waiver of informed consent - in the interest of facilitating potentially life-saving and life-enhancing research with protecting the rights and welfare of participants. For further information see: o OHRP Guidance: <http://www.hhs.gov/ohrp/humansubjects/guidance/hcdc97-01.htm> o FDA Guidance: <http://www.fda.gov/oc/ohrt/irbs/except.html>

Click "OK" below to return to the SmartForm page where you can select the appropriate response.

ID: IRB#12-001714

View: Display - Method Description

None of the above

Click "OK" below to return to the SmartForm page where you can select the appropriate response.

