Monitoring suicidal ideations: We will identify and monitor suicidal ideations using the SCID at baseline and the 3rd item of the Hamilton Depression Scale during each visit. Monitoring for SI will be done at each visit independent of the outcome assessment. Subjects with the score > 3 on admission signifying active suicidal ideations with or without a plan will be excluded from participation. We will call subjects between visits to monitor suicidal ideations. In case, of the persistent suicidal ideations, subjects will be discontinued from the study and referred to their primary physicians or psychiatrists, or to the clinical services at UCLA, or to the community psychiatrists for treatment and observation.

Elder abuse may be observed in the subject population of this study and will be appropriately reported. If any member of the research team has been informed of elder abuse, he or she is required to report it to the authorities. The obligation to report includes alleged or reasonably suspected abuse as well as known abuse.

3.0 *Indicate if any of the following are being obtained and used without any direct contact with study participants.

- Records (Not medical)

Human biological specimens

None of the Above

4.0 *Indicate all identifiers that may be **accessed or included in the research records** for the study:

Names

Dates

Age (if over 89 years)

Postal Address

Phone Numbers

Fax Numbers

E-Mail Address

Social Security Number

Medical Record Number

Health Plan Numbers

Account Numbers

License/Certificate Numbers

Vehicle ID Numbers

Device Identifiers/Serial Numbers

Web URLs

IP Address Numbers

Biometric Identifiers (including finger and voice prints)

Facial Photos/Images

Any Other Unique Identifier (this does not include the code assigned by the investigator to identify the data)

None of the above

4.1 **If social security numbers will be collected explain why they are necessary, how they will be used, how they will be protected and how long they will be retained.**

Social security numbers may be collected in order to issue a check request to pay the participants from UCLA Accounts Payable. The social security numbers will be written on a check request form and will not identify the subject as a participant for the study. The forms will be stored in a locked file cabinet and will be shredded and destroyed as soon as payment has been received (at the end of the duration of the study).

5.0 *Select all that apply:

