7) **Follow up assessment:** The follow up will take place weekly for the first 4 weeks of treatment and every 2 weeks for the remaining 5 months of the 6 months trial, followed by naturalistic follow up monthly up to 12 months. Each follow up assessment will include measures of efficacy and safety. The need for repeated assessments stems from our hypothesis of difference in time-to-remission occurring during the extension treatment. The weekly frequency of contact with all subjects will serve as an additional safeguard to monitor worsening of depression, as well as the emergence of side-effects or suicidal ideations. All assessment procedures described below are identical for the two groups. Most of the instruments have been administered in our ongoing studies, and our subjects age 60 and older tolerate their administration quite well (Table 2).

Primary outcomes will be measured and defined as follows: 1) Remission will be defined as HAM-D scores of 6 or less for 3 consecutive weeks, week 12 and at 6 months visit; 2) Depressive relapse is defined as an episode of major depressive disorder that occurs within 6 months after remission, while 3) recurrence is defined as another depressive episode that

occurs after 6 months have elapsed.

Assessment and monitoring of suicidal risk will occur at each visit and by phone between visits. We have applied the standard procedures that are required and approved by the UCLA Institutional Review Board. We have employed the same procedures in our ongoing studies of late-life depression since 1995, and have had no suicide attempts among our subjects. We will monitor suicidal ideations using the 3rd item of the Hamilton Depression Scale during each visit to the site and the Beck Scale of Suicidal Ideations (SSI). Monitoring for SI will be done at each visit independent of the outcome assessment.

Monitoring of expectations for symptomatic improvement: Since subjects will enter the treatment process for symptomatic improvement, we will account for a differences in expectations between the two groups. Thus, subjects' expectations for improvement will be assessed during the baseline visit, at week 12, at the end of the acute treatment trial (Week 24), and during follow up. We will control for any differences in the analyses.

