Inclusion criteria: 1) The presence of a major depressive disorder diagnosed according to the DSM-IVr criteria; 2) A 24-item Hamilton Rating Scale for Depression (HAM-D) score of 20 or higher at baseline; and 3) Mini-Mental State Exam (MMSE) score > 24; 4) Age > 60 years old; 4) Include participants after discontinuing anti-depressants during a washout period. The washout period will be performed at least 14 days before starting the study and between the administration of escitalopram and MAOI and other antidepressants; except fluoxetine (there will be a 4 week washout period).

5.0 *Indicate the specific exclusion criteria for each of the groups of research participants in this study.

If there are any exclusion criteria based on gender, pregnancy/childbearing potential, race, ethnicity or language spoken, explain the nature of and scientific rationale for the exclusions.

Exclusion criteria: subjects will be excluded if they had any current and/or lifetime history of other Axis I psychiatric disorders (except unipolar MDD; and stable comorbid anxiety disorders and insomnia), or recent unstable medical or neurological disorders; diagnosis of dementia; those with known allergic reactions to escitalopram or memantine. We will also exclude participants from taking all anti-depressant psychotropic medication and MAOIs for at least two weeks prior to entering the study (four weeks for fluoxetine). Escitalopram has low potential for interacting with most other drugs, including beta blockers, neuroleptics, lithium, and alcohol. The serotonergic syndrome has been reported in combined use of reversible MAOI, meclobomide, and linezolid, an antibiotic, which is a reversible non-selective MAOI. The washout period will be performed at least 14 days should be allowed between the administration of escitalopram and MAOI and other antidepressants; except fluoxetine there will be a 4 week washout period. We will not discontinue effective antidepressants. The taper will be instructed by the primary care physician or the psychiatrist.

6.0 *How (chart review, additional tests/exams for study purposes, etc.), when and by whom will eligibility be determined?

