Risks associated with memantine. The following Adverse Drug Reactions have been accumulated in clinical studies with memantine since its introduction in the market. Body as a whole – general disorders: Common-Headache; Uncommon-Fatigue; Psychiatric disorders: Common- Somnolence; Uncommon- Confusion, Hallucinations; Not known-Psychotic reactions; Gastro-intestinal system disorders: Common-Constipation; Uncommon-Vomiting; Not known Pancreatitis; Central & Peripheral nervous system: Common-Dizziness disorders; Uncommon- Gait abnormal; Very rare-Seizures. Overdose. There have been very few cases of overdose. In the case of an overdose (a suicide attempt), for which the highest memantine dose has been reported, the patient survived an oral intake of up to 400 mg memantine with effects on the central nervous system (that is, restlessness, psychosis, visual hallucinations, proconvulsiveness, somnolence, stupor, and unconsciousness) that resolved without permanent sequelae. Treatment of overdosage should be symptomatic.

Risks associated with combination of memantine and escitalopram. Combination of memantine with escitalopram is commonly used in clinical practice with rare side effects including increased anxiety and sleep disturbances. Dose modification is typically sufficient to lower the rate of side-effects.

Discontinuation from the study will be considered if subjects experience. We will monitor blood pressure and pulse once a week in the first four weeks, and at every visit. If any changes on the baseline ECG signifying ischemia occur, we will obtain additional tests of cardiac enzymes to rule out myocardial infarction (MI) (e.g., CK-MB; troponin). [name] is a part of the consulting and the DSMB teams and has advised us on the following parameters for discontinuation from the trial if cardiovascular complications arise. These include:

- a. Any changes in subject's physical complaints of a potentially vascular nature (e.g., angina or chest pain, fainting, dizziness, arrhythmia); increase in pulse over 10 beats per minute from baseline or tachycardia over 120 beats per min, changes in BP over 20 mm Hg;
- b. Changes on ECG or in cardiac enzymes indicating cardiac ischemia or a new onset arrhythmia;
- c. The development of any severe side-effects on the UKU Side Effect Rating scale rated as 3 or greater.

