All severe adverse events will be reported to the subjects and to their primary physicians and the UCLA IRB/ DSMB committee within 1 week of the PI's awareness, and within 2 weeks to the NIH.

- d. If a patient demonstrates worsening of their symptoms or no response by week 8 (i.e., less than 30% improvement in HAM-D scores or CGI score of > 4) of treatment, they will be discontinued from the study and referred for appropriate clinical services.
- e. The allowed dose range for MEM will be 5-20 mg/day; escitalopram 10-20 mg/day. If patients are not able to tolerate these medications, they will be discontinued from the trial.
- f. Suicidal ideations with the HAM-D item 3 score of 3 and greater, or worsening of the score on the Beck Suicidal Ideation scale.

All dropouts will be analyzed by the reason for termination and classified as: 1. Reasons: a) Lack of efficacy; b) Side-effects; c) Lost-to-follow up; d) Hospitalization; e) Death; f) Other
2. Relation to the study drug use: a) likely; b) probable; c) unlikely.

Structural and Functional Magnetic Resonance Imaging (s- and f-MRI) Scan. The risks or discomforts associated with MRI scans may include anxiety from being in a tight, enclosed space, or discomfort from staying still for too long. Should you become anxious or agitated during the MRI scan, this research study will be immediately discontinued. The sound of the MRI scanner can be loud. We will provide earplugs to minimize the noise, but some people find the noise annoying. The tests themselves can be boring or difficult, and you may get fatigued during the scan or from the diagnostic tests.

Occasionally subjects report having a headache, feeling stiff, or feeling anxious from claustrophobia after the scan.

The magnetism of the machine attracts certain metals; therefore, people with metals in them (specifically, pacemakers, infusion pumps, aneurysm clips, metal prostheses, joints, rods, or plates) will be excluded from the study. The "metal" in dental fillings is less susceptible to magnetism and is therefore allowed. The participant will be asked about any potential sources of metal, and you pockets will be emptied prior to the study. The participant may wish to stop the study at any stage, including the testing stage. Testing will last less than 15 minutes.

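### As printed, a patient scoring exactly 3 on HAM-D item 3 can be enrolled while already meeting a discontinuation criterion, and the formal exclusion list has no suicidality rule

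*Combined protocol and SAP*

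**What the plan says.** **Entry.** Section 9.2 (Information about Study Data), item 2.1, says that suicidal ideation will be identified with the SCID at baseline and with "the 3rd item of the Hamilton Depression Scale during each visit". It then gives the entry rule: "Subjects with the score > 3 on admission signifying active suicidal ideations with or without a plan will be excluded from participation". HAM-D item 3 is the only scored instrument named there, so the score must be the item 3 score.

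**Discontinuation.** Section 14.1, item 3.0, opens its list of criteria with "Discontinuation from the study will be considered if subjects experience". Criterion f in that list is "Suicidal ideations with the HAM-D item 3 score of 3 and greater, or worsening of the score on the Beck Suicidal Ideation scale". Section 15.2 repeats criterion f under item 5.1, which answers a question about defined rules for withdrawing participants.

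**Formal eligibility.** Section 11.1, item 5.0, asks for the specific exclusion criteria. The answer begins "subjects will be excluded if they had any current and/or lifetime history of other Axis I psychiatric disorders", with unipolar major depression and stable anxiety or insomnia exempted. It goes on to unstable medical or neurological illness, then "diagnosis of dementia; those with known allergic reactions to escitalopram or memantine", then the antidepressant washout. Neither this item, nor the inclusion criteria in item 4.0, nor the eligibility procedure in item 6.0 mentions suicidal ideation, plan or attempt.

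**Monitoring.** The follow-up text in section 10.1, item 4.0, covers checks during the trial: "We will monitor suicidal ideations using the 3rd item of the Hamilton Depression Scale during each visit to the site and the Beck Scale". It gives no entry threshold.

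**The concern.** The entry rule and the stopping criterion use the same item with cut-offs one point apart, and the entry rule is the looser of the two. Followed literally, the protocol lets a patient be randomised at a score at which it already contemplates stopping. Nothing in the documents explains why entry should be more permissive than continuation. The entry rule also describes what it means to exclude as active ideation whether or not there is a plan, which suggests a broad exclusion and fits a cut-off of 3 or greater better.

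The second problem is location. Randomisation and dispensing depend on confirming the eligibility criteria, and the natural place to look for those is section 11.1. Someone working from that section finds no suicidality rule. No other listed criterion covers the gap: the Axis I exclusion exempts unipolar major depression, and the escitalopram entry in section 8.6 lists suicidal ideation among the symptoms of a major depressive episode.

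What is at stake is participant safety. All entrants have major depression with a HAM-D of at least 20, and section 14.1 itself notes that suicide rates are highest in the elderly.

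**Working it through.** The plan states no numerical result on this point. The check is a comparison of integer cut-offs and a reading of the eligibility text.

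**Inputs**
- Entry exclusion as printed (section 9.2, item 2.1): item 3 score > 3.
- Discontinuation criterion (sections 14.1 item 3.0 and 15.2 item 5.1, criterion f): item 3 score ≥ 3.
- Alternative reading of the entry rule: item 3 score ≥ 3.

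**Step 1: compare the cut-offs.** Here, admitted means not excluded by this rule.

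| Item 3 score | Entry excludes > 3 (printed) | Entry excludes ≥ 3 | Discontinuation criterion |
|---|---|---|---|
| 2 or less | admitted | admitted | not met |
| 3 | admitted | excluded | met |
| above 3 | excluded | excluded | met |

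As printed, the scores both admissible and at the criterion are {≤ 3} ∩ {≥ 3} = {3}. With entry excluding ≥ 3, they are {≤ 2} ∩ {≥ 3}, which is empty. The documents do not give the top of the item's range, and the result does not depend on it.

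**Step 2: could the sign be a slip?** Strict signs are used loosely elsewhere.
- Age is printed as > 60 in section 11.1, item 4.0, but as 60 and older in the lay summary (section 2.2).
- Remission is printed as HAM-D < 6 in the power analysis (section 10.1, item 6.0), but as 6 or less in the outcome definition (section 10.1, item 4.0).
- The MMSE must be > 24 for inclusion (section 11.1, item 4.0), while the automatic exclusion is < 24 (section 11.1, item 6.0, and section 10.1, item 4.0). A score of 24 falls under neither.

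An intended ≥ 3 is therefore plausible, and under that reading sections 9.2, 14.1 and 15.2 agree. The text cannot settle which was meant.

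**Step 3: look for the rule in section 11.1.** Items 4.0, 5.0 and 6.0 contain no suicidality criterion. This holds whichever sign was intended in section 9.2.

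**The case against.** The best reply is that the threshold conflict may not exist in the source. Given the pattern in step 2, the printed sign may be careless usage or a character lost when the text was read from PDF, and a reading loss is not an error in the plan. This is a fair caution. It limits the claim to what is printed and lowers confidence about intent. It does not reconcile the two cut-offs.

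Discontinuation at 3 is also introduced as something to be considered, so a patient scoring 3 may only trigger a review. That softens the conflict, but section 15.2 repeats the criterion under defined withdrawal rules, and a newly enrolled patient would meet it at once.

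On location, the form in section 9.2 gives suicidal ideation as an example of information that ethically requires action, so the answer was prompted there, and all sections belong to one application. The exclusion does exist. The investigator determines eligibility and is responsible for the SCID. The telephone script and grant protocol are attachments not reproduced here and may carry the rule. These points stand: how staff actually screen is not described fully enough to say that the rule would be missed. Even so, the item that asks for exclusion criteria should contain this one.

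Finally, the SCID, item 3 and the Beck scale at visits, calls between visits, and discontinuation for persistent ideation are real safeguards under either sign. They reduce the risk but do not supply a clear entry rule.

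**Conclusion.** The concern holds as stated. As printed, entry excludes only item 3 scores above 3, discontinuation is considered from 3, and section 11.1 has no suicidality rule. One score value, 3, is affected. How many patients that means is unknown and may be none, because no baseline distribution of item 3 is given. The threshold point rests on reading the printed sign literally; if an inclusive sign was meant, the three sections agree and only the omission from section 11.1 remains. No effect on the primary comparison, power or sample size is claimed. Because this is a safety threshold that misfires if followed as written, and the correction is short, it should be made. Confidence is medium, given the doubt about the sign.

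**What to change.** In section 9.2, item 2.1, replace the symbol with words: exclude patients with a HAM-D item 3 score of 3 or greater at admission, matching criterion f in sections 14.1 and 15.2. Add the same sentence to the exclusion criteria in section 11.1, item 5.0.

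The cost is protocol wording in two places. Patients scoring exactly 3 become ineligible, which should be a small number at most. Sample size and analysis are unchanged.
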